The Effects of Music and Auditory Beat Stimulation on Anxiety Study Protocol

Approved by the Ryerson Ethics Board: REB 2020-068 on March 26th, 2020, renewal
approval: March 18th, 2021

NCT#:

Date: 2021-11-26

Study Protocol

Participants

Participants (n=318) who are taking anti-anxiety medication will be recruited from Prolific, an online research recruitment platform. A power analysis was conducted drawing effect sizes from a previous study that examined how anxiety levels (measured by the STAI), were affected under the following experimental conditions: binaural beats, music with binaural beats and no-intervention (Padmanabhan et al., 2005). The power analysis indicated that to achieve a power of 0.80 at a significance of $p = 0.05$, a minimum of 45 participants in each treatment group are required (Padmanabhan et al., 2005). An additional 10 participants will be recruited to account for potential participant attrition. Participants will be pre-screened for moderate to severe anxiety using the STICSA trait questionnaire (Grös, Antony, Simms, & McCabe, 2007). Participants will then be randomly assigned to one treatment arm.

Experimental treatment conditions

Each of the experimental treatment conditions below will be 24 minutes in duration, as this seems to be the exposure time needed for binaural beats to reduce anxiety levels and for general effectiveness of binaural beats in other areas such as cognition (Garcia-Argibay, 2019; Isik et al., 2017).

1. Pink noise (control condition)
2. Theta ABS
3. Theta ABS with music generated by LUCID's calm mode
4. Music generated by LUCID's calm mode

Procedure

After reading and signing the consent form and going over experimental expectations, participants will be asked to fill out the Short Test of Music Preferences (STOMP), Queen's Music Questionnaire, the Positive and Negative Affect Scale (PANAS), Self-Assessment Manikin (SAM), Eysenck Personality Questionnaire and the STICSA state version. Participants will then undergo their respective listening condition. After undergoing experimental treatment, participants will complete the following questionnaires: STICSA state version, SAM and the PANAS.

Outcome measures and questionnaires

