Participants show a more pleasurable emotional response to their own preferred music compared to experimenter-selected music (Davis & Thaut, 1989; Thaut & Davis, 1993). We therefore decided to incorporate the Short Test of Music Preferences (STOMP) as a covariate in our analyses (Rentfrow & Gosling, 2003). The Queen's Music Questionnaire will be administered to assess musical education and daily music exposure of each participant, which will be used as a covariate in our analyses. The Eysenck Personality Questionnaire will be used to determine participants' extraversion and introversion (Rocklin & Revelle, 1981). The State Trait Inventory for Cognitive and Somatic Anxiety (STICSA) will be used to pre-screen high trait anxiety participants (trait version) for participation in this study (Grös et al., 2007).

The state version of STICSA will be used to assess state anxiety before and after experimental treatment. This will serve as the primary outcome measure. The Positive and Negative Affect Scale (PANAS) will be used to assess mood (Watson, Clark, & Tellegen, 1988) before and after experimental treatment. The Self-Assessment Manikin (SAM)

questionnaire will be used to assess valence and arousal of the participant before and after experimental treatment (Bradley & Lang, 1994).

References

Bradley, M. M., & Lang, P. J. (1994). Measuring emotion: The self-assessment manikin and the semantic differential. *Journal of Behavior Therapy and Experimental Psychiatry*, 25(1), 49-59. doi:[https://doi.org/10.1016/0005-7916\(94\)90063-9](https://doi.org/10.1016/0005-7916(94)90063-9)

Davis, W. B., & Thaut, M. H. (1989). The Influence of Preferred Relaxing Music on Measures of State Anxiety, Relaxation, and Physiological Responses. *Journal of Music Therapy*, 26(4), 168-187. doi:10.1093/jmt/26.4.168

Garcia-Argibay, M. (2019). Efficacy of binaural auditory beats in cognition, anxiety, and pain perception: a meta-analysis. *Psychological Research*, 83(2), 357-372. doi:10.1007/s00426-018-1066-8

Grös, D. F., Antony, M. M., Simms, L. J., & McCabe, R. E. (2007). Psychometric properties of the State-Trait Inventory for Cognitive and Somatic Anxiety (STICSA): Comparison to the State-Trait Anxiety Inventory (STAI). *Psychological assessment*, 19(4), 369.

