**The Effects of Music and Auditory Beat Stimulation on Anxiety
Statistical Analysis Plan**

Approved by the Ryerson Ethics Board: REB 2020-068 on March 26th, 2020, renewal
approval: March 18th, 2021

NCT#:

Date: 2021-11-26

Statistical Analysis Plan

For each participant the post-experimental treatment STICSA, PANAS and SAM Valence and arousal scores will be subtracted from the pre-experimental treatment scores. Shapiro-Wilks normality and homogeneity of variances tests will be done on the STICSA, PANAS and SAM datasets, and homogeneity of covariances tests will be done on music preferences, and personality type datasets to determine if assumptions of the Multivariate Analysis of Covariance (MANCOVA) are satisfied. If these assumptions are satisfied, a MANCOVA over the factor of experimental condition will be performed with music preferences, spontaneous blink rate and personality type as covariates and the relative differences (Pre-treatment – Post-treatment) of STICSA, PANAS and SAM Valence and arousal scores as dependent variables. Post-hoc Tukey's HSD multiple comparisons tests will be done comparing the LUCID music with theta ABS condition with all of the other experimental conditions. Further post-hoc Tukey's HSD multiple comparisons tests will be done comparing the theta ABS and LUCID music conditions with the pink noise condition. Statistically accounting for music preferences, spontaneous blink rate, personality type, age and gender as covariates should reduce some variability in the analysis.

If the data do not satisfy the assumptions for the MANCOVA, permutations tests, specifically the ImPerm package in R will be used to conduct a permutation version of the repeated measures ANCOVA for each dependent variable (STICSA Somatic, STICSA Cognitive, Positive Affect (PANAS), Negative Affect (PANAS) and SAM Valence and arousal scores), with time (pre and post intervention) as the within subjects variable and experimental condition as the between subjects factor. Post-hoc permutation tests will be done comparing the LUCID music with theta binaural beats condition with all of the other experimental conditions for each dependent variable. Permutation tests are a good way to control the type I error rate for multiple comparisons, it is non-parametric and so makes no assumptions about the underlying distribution of the data that are common in other inferential statistical tests (Camargo, Azuaje, Wang, & Zheng, 2008; Good, 1994; Kuehl, 2000).

References

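### Neither analysis path adjusts for the baseline STICSA, PANAS and SAM scores already collected: an avoidable loss of precision, not a bias

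*SAP*

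**What the plan says.** The first paragraph of the SAP forms a change score for every outcome: "the post-experimental treatment STICSA, PANAS and SAM Valence and arousal scores will be subtracted from the pre-experimental treatment scores". The MANCOVA then has "the relative differences (Pre-treatment – Post-treatment) of STICSA, PANAS and SAM Valence and arousal scores as dependent variables". Its covariates are given in the same sentence: "a MANCOVA over the factor of experimental condition will be performed with music preferences, spontaneous blink rate and personality type as covariates". The last sentence of that paragraph gives a longer list and its purpose: "Statistically accounting for music preferences, spontaneous blink rate, personality type, age and gender as covariates should reduce some variability in the analysis". The Protocol (Outcome measures and questionnaires) also names the Queen's Music Questionnaire as a covariate alongside the STOMP. No list in either document includes a baseline outcome score.

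The second paragraph of the SAP gives the fallback, a permutation repeated-measures ANCOVA for each outcome, "with time (pre and post intervention) as the within subjects variable and experimental condition as the between subjects factor". It names no covariates and does not say which model term is the test of interest.

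The baseline scores exist. Under Procedure, the forms completed before listening include "the Positive and Negative Affect Scale (PANAS), Self-Assessment Manikin (SAM), Eysenck Personality Questionnaire and the STICSA state version". The Protocol makes state STICSA the primary outcome: "The state version of STICSA will be used to assess state anxiety before and after experimental treatment".

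**The concern.** Subtracting the post score from the pre score uses the baseline with its slope fixed at 1. It does not adjust for baseline, because the slope is not estimated from the data. In large samples, an analysis that estimates the slope is at least as precise at any pre-post correlation. An outcome's own baseline is the obvious covariate for the SAP's stated aim of reducing variability, and it is the one left out.

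Validity is not at stake. Under random assignment the change-score contrast is unbiased over repeated randomisations. In any one sample, though, a chance baseline difference between arms moves the change-score contrast by about (1 − ρ) per unit of that difference when the pre and post SDs are equal, where ρ is the pre-post correlation. Baseline adjustment removes this. The price of leaving it out is wider intervals and lower power from the same participants.

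**Working it through.** **Inputs.** From the Protocol, Participants: 318 in total, a minimum of 45 per group, power 0.80, significance level 0.05. Four conditions are listed, so equal arms would hold 318/4 = 79.5; 79 is used below. Assumed, because the documents do not give them: ρ of 0.5, 0.7 or 0.9; k = post SD / pre SD of 0.8, 1 or 1.2; equal allocation; no losses; two-sided tests.

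**The plan's own figure.** The 45 per group cannot be reproduced, since no effect size, SD or test is stated. Working backwards, a two-sided two-sample t-test has power 0.80 at 45 per group for d = 0.597.

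**The fallback.** With two time points, the term that compares change between conditions is time-by-condition, and its test is the one-way test on change. On simulated data (N = 316), the one-way F on change was 4.975. The time-by-condition F was also 4.975, and stayed at 4.975 with a time-constant covariate not crossed with time. The variance comparison below therefore applies to both paths.

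**Variance ratio.** With pre SD s:

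- Change score: s²(1 + k² − 2ρk)
- Baseline-adjusted: s²k²(1 − ρ²)
- Ratio: k²(1 − ρ²)/(1 + k² − 2ρk), which is (1 + ρ)/2 when k = 1

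Example at k = 1, ρ = 0.5: 0.75/1 = 0.75.

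**Cost of six covariates.** Estimating six slopes with 318 participants in four arms inflates variance by (318 − 4 − 1)/(318 − 4 − 6 − 1) = 313/307 = 1.020. Each cell shows the gross ratio, then the ratio after this cost.

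| k | ρ = 0.5 | ρ = 0.7 | ρ = 0.9 |
|---|---|---|---|
| 1.0 | 0.750 / 0.765 | 0.850 / 0.867 | 0.950 / 0.969 |
| 1.2 | 0.871 / 0.888 | 0.966 / 0.985 | 0.977 / 0.996 |
| 0.8 | 0.571 / 0.583 | 0.628 / 0.640 | 0.608 / 0.620 |

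A simulation (four arms of 79, six outcomes intercorrelated at 0.4, all six baselines fitted, k = 1, 6,000 runs) gave 0.755, 0.867 and 0.970. In standard-error terms, the gross gain at k = 1 is 1 − √0.75 = 13%, 1 − √0.85 = 8% and 1 − √0.95 = 2.5%.

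**Power at 79 per arm** (k = 1; adjusted d = d/√((1 + ρ)/2); one baseline covariate; unadjusted two-sided pairwise test):

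| Effect in change SDs | Change score | ρ = 0.5 | ρ = 0.7 | ρ = 0.9 |
|---|---|---|---|---|
| 0.449 (0.80 power at 79 per arm) | 0.80 | 0.90 | 0.86 | 0.82 |
| 0.597 (0.80 power at 45 per arm) | 0.96 | 0.99 | 0.98 | 0.97 |

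With the four-group Tukey criterion, the d = 0.597 row becomes 0.88 on change, rising to 0.96, 0.93 or 0.90.

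**Bias.** In a simulation with four arms of 45 and 4,000 runs at ρ = 0.5, the true effect was 0.591 and the mean estimates were 0.594 (change) and 0.595 (adjusted). At ρ = 0.7 the true effect was 0.457 and the means were 0.464 and 0.463. Neither analysis shows material bias.

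**The case against.** The strongest reply is that this is a preference for efficiency. A prespecified change-score analysis of a randomised trial answers the question asked, and the gain cannot be sized from the documents. That is right about validity, and it is why the point ranks as an improvement the plan should make and not as an error that undermines it.

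- **The net gain can vanish.** At k = 1.2 the variance cut after six covariates is about 11%, 1.5% and 0.4%. At k = 1.2 and ρ = 1/1.2 = 0.83 the baseline slope is exactly 1, so there is no gross gain and the six covariates cost about 2%. This stands, but 2% bounds the loss, while the table's largest net gain is about 42%.
- **A high correlation does not always mean a small gain.** At k = 0.8 and ρ = 0.9 the gross cut is 39%. This stands, and it strengthens the case for adjusting.
- **The SAP plans Tukey comparisons, and the main power figures use unadjusted tests.** Under Tukey, the gain for the larger effect is 2 to 8 points and not 1 to 3.
- **The fallback is called an ANCOVA without naming covariates, so baseline adjustment is unspecified and not excluded.** This is fair as a reading of the text. But with the pre score as a level of time, it would not normally be a covariate as well. If other covariates were crossed with time, the test would be a covariate-adjusted analysis of change, still without the outcome's own baseline.
- **The planned covariates are left out of the calculation.** Any that correlate with baseline could shrink the gain. The documents do not allow this to be sized.

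**Conclusion.** The concern holds. Neither path specifies adjustment for the outcome's own baseline, although every baseline needed is collected. The planned contrasts remain valid and unbiased under randomisation; the loss is one of precision.

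With equal SDs and correlations of 0.5 to 0.7, the net variance reduction in the MANCOVA is about 24% to 13%, and at 0.9 it is about 3%. With a post SD 20% above the pre SD it is about 11% or less; with a post SD 20% below, it is about 36% to 42%. At 318 participants the power gain for an effect as large as the 45-per-group minimum implies is modest. It is larger for smaller effects and under the planned Tukey criterion. These sizes rest on the assumed correlation and SD ratio, equal arms without losses, and no allowance for the covariates already planned. The conclusion that baseline adjustment should be specified does not depend on any one of those values.

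**What to change.** - **MANCOVA.** Add the baseline scores of the outcomes as covariates: six by the fallback's list, namely STICSA somatic and cognitive, PANAS positive and negative, and SAM valence and arousal. State that the Tukey comparisons use the baseline-adjusted condition means for each outcome.
- **Fallback.** Replace the time-by-condition model with a permutation ANCOVA of the post score on condition, with that outcome's own baseline as covariate. State how the permutation is done and which other covariates stay in the model.
- **Assumption checks.** Extend the SAP's checks to the added covariates, including whether the baseline slopes are similar across conditions.

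The cost is SAP text and no new data: six degrees of freedom in the MANCOVA, roughly 2% in variance at 318 participants, and one degree of freedom per outcome in the fallback. The change should be dated and made before outcome data are seen, since a covariate added later would look data-driven. The documents do not show whether that is still possible. If it is not, the baseline-adjusted analysis should be reported as a labelled sensitivity analysis beside the planned one.

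### STICSA state is the declared primary outcome, but the SAP names no primary test of it and no rule for its two subscales in the fallback

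*SAP*

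**What the plan says.** **Primary outcome.** In Outcome measures and questionnaires, the protocol says of the state version of the STICSA: "This will serve as the primary outcome measure". It does not say whether that means a total or subscales.

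**Main path (SAP, first paragraph).** One MANCOVA over experimental condition takes the pre-minus-post differences "of STICSA, PANAS and SAM Valence and arousal scores as dependent variables". The follow-up reads: "HSD multiple comparisons tests will be done comparing the LUCID music with theta ABS condition with all of the other experimental conditions". A second set of Tukey tests is described as "comparing the theta ABS and LUCID music conditions with the pink noise condition". Neither sentence names a dependent variable or says whether the tests depend on a significant MANCOVA.

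**Fallback (SAP, second paragraph).** If the MANCOVA assumptions fail, a permutation repeated measures ANCOVA is run "for each dependent variable (STICSA Somatic, STICSA Cognitive, Positive Affect (PANAS), Negative Affect (PANAS) and SAM Valence and arousal scores". Post-hoc permutation tests are then made "comparing the LUCID music with theta binaural beats condition with all of the other experimental conditions for each dependent variable". The only remark on multiplicity is a general one: permutation testing is a good means of controlling type I error over multiple comparisons. No joint procedure, alpha split or ranking of outcomes is given.

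**The concern.** Naming an instrument as primary does not define a primary analysis. A reader of the SAP cannot tell which STICSA score, test, contrast or subscale rule decides whether the trial succeeded. Two analysts following the text could report different primary results from the same data.

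The two paths leave this open in different ways. In the main path, the one test clearly specified is multivariate, and mood or arousal can make it significant without any effect on anxiety. In the fallback, STICSA becomes two separately tested outcomes with three arm contrasts each, and a favourable result on any of them could be presented as the primary finding. The list of contrasts also changes with the path.

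**Working it through.** **Inputs.** From the documents: four arms; alpha 0.05 (stated only for the power analysis); a minimum of 45 per group; 318 in total, so 318/4 = 79.5, taken as 79 per arm. Assumed, because the documents give none: all correlations, the effect size, normal data and no covariates.

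**The plan's own figure.** The effect size behind 45 per group is not stated, so the figure cannot be reproduced directly. A four-arm F test with f = 0.25 has power 0.804 at 45 per group, so f = 0.25 is used below. With one arm differing from the other three, f = d × √(3/16), so d = 0.25/0.433 = 0.577.

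**Contrasts by path.** Main path: the combination arm against each of three arms, plus theta ABS and LUCID music each against pink noise, 3 + 2 = 5. Fallback: the first three only. With two subscales the fallback therefore makes 3 × 2 = 6 STICSA contrasts.

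**Lead test.** If only SAM arousal responds (f = 0.25, 79 per arm, correlations among the other outcomes 0 to 0.5), simulation with Wilks' lambda finds the MANCOVA significant in roughly 76–98% of trials. STICSA has no effect in any of them.

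**Fallback, false-positive risk for STICSA when nothing works.** For two independent tests: 1 − (1 − 0.05)² = 0.0975. For six: 1 − 0.95⁶ = 0.265, an upper guide only, because contrasts that share an arm are correlated. Simulated values by correlation between the subscales:

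| What would count as a STICSA finding | 0 | 0.5 | 0.7 |
|---|---|---|---|
| Condition test at 0.05 on either subscale | 9.8% | 9.2% | 8.5% |
| Any of three unadjusted contrasts, either subscale | 23.5% | 22.0% | 20.3% |

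For any of three unadjusted contrasts on a single score, the risk is about 12.5–12.6% (1 − 0.95³ = 14.3% if they were independent). Permutation tests on simulated change scores (999 permutations) gave matching results. The working ranges are 8.5–9.8%, 20–24% and 12–13% respectively.

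**Main path, false STICSA claim.** Same scenario (only SAM arousal responds, 79 per arm), Tukey critical value on the five contrasts:
- One STICSA score: 4.1–4.3% if Tukey requires a significant MANCOVA, 4.3% if it does not. Tukey covers all six pairs of arms at 5% and the plan uses five.
- Two subscales correlated 0.5–0.7: 7.1–8.0% over both readings. This applies only if STICSA in the first paragraph means two scores, which the SAP does not say.

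**The permutation remark.** A permutation test run on one contrast of one outcome gives a valid p-value for that contrast and outcome. Running several separately does not control the chance that at least one is falsely significant. A joint procedure such as max-T does: in simulation, max-T over the three contrasts on a STICSA total held the error at about 5%. Applied within each of two subscales at 0.05, it left 9–10%.

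**The case against.** The best defence is that STICSA-specific tests are already implied. Tukey's HSD works on one variable at a time, so its use after a MANCOVA suggests a follow-up per outcome, and the fallback explicitly analyses each outcome. That stands. A reader might infer that the plan never tests STICSA, or that the main path inflates its error. The documents do not support either. With one score the error stays under 5%, and what is lacking is the designation.

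The 76–98% should also not be read as a rate of false anxiety claims. It is the MANCOVA correctly detecting an arousal effect. It shows only that this test cannot serve as the test of the primary outcome.

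The fallback percentages depend on rules the SAP does not state. A reader might infer that an either-subscale claim or unadjusted contrasts are planned. The text is silent, so the figures measure what the silence permits.

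On the permutation remark, multiple comparisons may mean arms rather than outcomes, and one reference cited for it concerns permutation tests for multiple hypotheses, so a joint method may be intended. On either meaning none is named, and separate tests do not supply it.

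Finally, because "normality and homogeneity of variances tests will be done on the STICSA, PANAS and SAM datasets", a reader might infer that PANAS or SAM distributions bias the STICSA result by triggering the fallback. Checking every dependent variable is ordinary for a MANCOVA, and no effect of the switch on STICSA error or power has been shown.

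**Conclusion.** The concern holds as a missing definition with a real error consequence in the fallback. The protocol's primary outcome has no designated score or test in the SAP, its two fallback subscales have no decision rule, the fallback contrasts have no named adjustment, and the contrasts differ between paths (five against three).

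The textual gap needs no simulation. The size of the fallback risk rests on assumed correlations of 0 to 0.7, normal data without covariates, and success rules left open. In the main path with one STICSA score there is no inflation. This should be corrected before the outcome data are analysed. It does not show that the trial is invalid.

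**What to change.** 1. Designate one STICSA-state primary score, for example the change in the total, and use it in both paths.
2. Make the effect of condition on that score, at 0.05, the primary test: a univariate ANCOVA, or its permutation version in the fallback. Alternatively, name one contrast, such as LUCID music with theta ABS against pink noise, as the success criterion. This suits the trial better if that comparison is the main question, because a test over all four arms can be significant without it.
3. Use the same five contrasts in both paths, adjusted within that score: Tukey, or max-T in the permutation path. The figure of about 5% for max-T was obtained with equal variances. With one arm's SD assumed 1.5–2 times the others, a pooled-variance max-T over five contrasts at 79 per arm ran at about 6.1–7.3%, so the statistic should be specified with unequal variances in mind.
4. If both subscales stay primary, either require both at 0.05, or use 0.025 for each and apply the same 0.025 to the adjusted contrasts within each subscale (0.025 + 0.025 = 0.05).
5. Label PANAS and SAM secondary and the MANCOVA supportive.
6. Replace the permutation remark with the named joint procedure, or state that no control across secondary outcomes is claimed.

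**Cost.** The SAP text changes and no new data are needed. Mood and arousal results can no longer carry the main claim, and a two-subscale rule costs some power. Assuming f = 0.25 on both subscales, correlated 0.5–0.7:

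| Rule | 79 per arm | 45 per arm |
|---|---|---|
| Total score at 0.05 | 0.99 | 0.87–0.91 |
| Either subscale at 0.025 | 0.98–0.99 | 0.83–0.86 |
| Both subscales at 0.05 | 0.95 | 0.69–0.71 |

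A contrast criterion also costs power. For a score with f = 0.25, the condition test has power 0.97 at 79 per arm and 0.80 at 45, against 0.85 and 0.56 for one Tukey-adjusted contrast.

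### The SAP fixes five pairwise comparisons in advance but tests them with Tukey's HSD, without saying that they use covariate-adjusted means and the matching standard errors

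*SAP*

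**What the plan says.** The first paragraph of the SAP describes a MANCOVA on the pre-minus-post differences, with experimental condition as the factor and with covariates, to be used if its assumptions hold. Two sentences on pairwise tests follow. The first concerns the combination arm and gives three comparisons:

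- "Post-hoc Tukey's HSD multiple comparisons tests will be done comparing the LUCID music with theta ABS condition with all of the other experimental conditions"

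The second concerns the two single components and gives two more:

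- "Further post-hoc Tukey's HSD multiple comparisons tests will be done comparing the theta ABS and LUCID music conditions with the pink noise condition"

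The paragraph closes by giving the purpose of the covariates. It lists music preferences, blink rate and personality type, and says that accounting for these together with "age and gender as covariates should reduce some variability in the analysis".

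None of these sentences says which means the Tukey tests compare, which error variance they use, or whether the two sets of comparisons form one family.

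The second paragraph covers the case where the assumptions fail. Permutation tests then replace Tukey's HSD, and only the three comparisons of the combination with the other arms are named.

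**The concern.** An overall MANCOVA test does not show which arms differ. It is therefore reasonable to expect the pairwise comparisons to carry the conclusions about the combination, the beats and the music, although the documents name no contrast as primary. Two features of the text then matter.

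First, Tukey's HSD as classically defined compares independent, unadjusted arm means. An analyst who runs the textbook procedure on the change scores leaves out the covariates that the SAP includes to reduce variability. An analyst who applies the Tukey adjustment to adjusted means keeps them. Both could claim to have followed the SAP, and the choice should not stay open until the data are seen.

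Second, Tukey's HSD controls the error rate over every pair of arms. The SAP does not ask for theta ABS versus music, so some protection is spent on a comparison nobody plans to make. The single-step form also gives up the power that a step-down test would add at the same family-wise error.

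**Working it through.** **Inputs from the documents.** There are four arms. The Protocol (Participants) aims "to achieve a power of 0.80 at a significance of" 0.05, with sidedness not stated (two-sided assumed here). It says that "a minimum of 45 participants in each treatment group are required". It plans 318 participants in total, which is 318 / 4 = 79.5 per arm if allocation is equal (ratio not stated); 79 is used below.

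**Inputs not in the documents.** No effect size is given. The Protocol says only that the calculation was made by "drawing effect sizes from a previous study that examined how anxiety levels (measured by the STAI), were affected". The share of variance explained by the covariates (R²) is not given either. Both are assumptions below.

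**Step 1: the plan's own figure.** Without an effect size, 45 per arm cannot be reproduced. Back-solving a two-sided comparison of two means, normal approximation:

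d = (1.960 + 0.842) × √(2/45) = 0.59

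This value is used as a reference. It is not a figure from the plan.

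**Step 2: the count.** Four arms give 4 × 3 / 2 = 6 pairs. The SAP names 3 + 2 = 5. The missing pair is theta ABS versus music.

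**Step 3: critical values.** The Tukey critical |t| is the 95% point of the studentised range for four means, divided by √2. The exact value for the five contrasts comes from simulating the maximum |t| over those five.

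| Method, 45 per arm, 176 df | Critical \|t\| | Power per pair, d = 0.59 |
|---|---|---|
| Tukey, six pairs | 2.594 | 0.583 |
| Bonferroni, five | 2.604 | 0.579 |
| Single-step max-t, five | 2.539 | 0.604 |

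At 79 per arm (312 df) the powers are 0.870, 0.868 and 0.881. Protecting the sixth pair therefore costs 0.604 − 0.583 = 2.1 points at 45 per arm and 0.881 − 0.870 = 1.1 points at 79. Bonferroni over the five would do slightly worse than Tukey.

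**Step 4: whether the covariates reach the contrasts.** Power is taken from the noncentral t with noncentrality d × √(n/2) / √(1 − R²) and the Tukey critical value. The few degrees of freedom used by the covariates are ignored.

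| R² (assumed) | 45 per arm | 79 per arm |
|---|---|---|
| 0 (covariates left out) | 0.583 | 0.870 |
| 0.1 | 0.640 | 0.907 |
| 0.2 | 0.704 | 0.941 |
| 0.3 | 0.774 | 0.968 |

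Leaving the covariates out costs 5.7, 12.1 and 19.1 points at 45 per arm, and 3.7, 7.1 and 9.8 points at 79.

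**Step 5: stepping down.** Tukey's HSD was compared by simulation with a step-down max-t test of the five contrasts, both at 5% family-wise error and both without covariates. Arm means are assumed, in SD units, in the order pink noise, theta ABS, combination, music.

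| Arm means | n per arm | Contrast | Tukey | Step-down max-t |
|---|---|---|---|---|
| 0, 0, 0.6, 0 | 45 | combination vs each other arm | 0.60 | 0.65 to 0.66 |
| 0, 0, 0.6, 0 | 79 | combination vs each other arm | 0.88 | 0.91 |
| 0, 0.3, 0.6, 0.3 | 79 | combination vs one component | 0.24 | 0.32 |
| 0, 0.3, 0.6, 0.3 | 79 | combination vs pink noise | 0.88 | 0.90 |

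Most of this gain comes from stepping down. In the first row, moving to single-step max-t on five contrasts gives 0.62. In the third row it gives 0.26.

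**The case against.** The strongest reply is that the SAP nowhere says the Tukey tests use raw means. They follow directly after the MANCOVA as its post-hoc step, and the next sentence speaks of covariates reducing variability in the analysis. The Tukey-Kramer adjustment can be applied to covariate-adjusted means with the model's error variance, and on that reading nothing is lost. This stands. A reader might infer that the covariates are shown not to reach the contrasts, but the documents support only that the SAP does not say.

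A reader might also infer that the error rate is inflated. If raw means were combined with the adjusted residual error, family-wise error would be 0.070, 0.098 and 0.137 at R² of 0.1, 0.2 and 0.3. That arithmetic is right, but nothing in the SAP specifies that mixture. These figures describe a possible slip, not this trial's error rate.

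Finally, Tukey's HSD is not without benefit. Applied to adjusted means it controls family-wise error within an outcome, and its simultaneous intervals agree with its decisions. Choosing a step-down test is a choice between valid methods, and the larger step-down gains rest on patterns of means for which the documents give no basis. This also stands, and it limits the multiplicity part of the point to a modest, inexpensive gain in power.

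**Conclusion.** The point holds as an ambiguity with an inexpensive remedy, and it concerns the MANCOVA branch. The SAP names five of six pairs in advance, assigns them a procedure built for all six, and does not tie them to the covariate-adjusted model.

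The larger stake is the covariates: about 6 to 19 points of power per pair at 45 per arm and about 4 to 10 at 79, for d = 0.59 and R² between 0.1 and 0.3. Both d and R² are assumed, and the loss arises only if the analyst works with unadjusted means.

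The multiplicity stake is smaller. The sixth pair costs about 1 to 2 points. A step-down test of the five brings the total gain over Tukey to about 3 to 8 points for combination versus component and about 1 to 6 against pink noise, depending on the assumed means. The documents do not support a claim that the planned tests are invalid, or that the all-pairs adjustment by itself costs much power.

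**What to change.** Replace both Tukey sentences with wording such as:

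> For each outcome, the five named contrasts will be estimated as differences in covariate-adjusted means from the ANCOVA, with the matching standard errors, and tested as one family with a max-t (multivariate t) procedure at two-sided 5%, step-down for decisions and single-step for simultaneous intervals.

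List the covariates of that model once. The closing sentence of the paragraph adds age and gender, which the sentence specifying the MANCOVA does not include. Name the same five contrasts in the permutation branch, so that the questions tested do not depend on the outcome of the assumption checks.

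The cost is a few sentences and a few lines of code, with no new data and no change to the design. One downside should be stated: step-down decisions can be slightly stronger than the single-step intervals reported beside them. If full agreement is preferred, single-step max-t on the five contrasts gives it and still has a smaller critical value than Tukey (2.54 against 2.59 at 45 per arm). The change controls error within each outcome and does not address multiplicity across outcomes.
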